Primary Endpoint	
 ▪ Proportion of patients with undetectable serum PSA (< 0.2 ng/mL) at 6 months following completion of apalutamide therapy (18 months from date of randomization).
Secondary Endpoints	
 1. Time to PSA progression by PCWG criteria 2. Feasibility and Safety of apalutamide and concurrent SBRT
Exploratory Endpoints	
 1. Association between genomic factors and presence of oligometastatic disease 2. Association between somatic and germline genomic alterations with clinical outcomes Note: The italicized objectives above were discontinued in Protocol v. 8.0. See Section 7.3 for additional information. 3. Association between baseline PSMA-PET scan uptake and distribution of lesions with treatment outcomes.
Statistical Analysis/ Sample Size Justification	The primary efficacy is based on the primary endpoint of the study, the proportion of patients with undetectable PSA (PSA < 0.2 ng/mL) 6 months following completion of 12 months of apalutamide therapy (18 months from date of randomization). Assuming a 10% inevaluable/drop-out rate per treatment arm, a sample size of 60 patients (30 patients/arm) provides 84% power to detect a difference in proportion of patients with undetectable PSA of 25% in the apalutamide + SBRT arm vs. 2.5 % in the apalutamide monotherapy arm, with a unidirectional level of significance of 0.10 (Fisher's exact test). Patients who discontinue apalutamide prior to completion of 12 months of therapy for reasons other than disease progression by PCWG criteria will be considered inevaluable for this analysis.

List of Abbreviations

AE	adverse event
ALP	alkaline phosphatase
ALT	alanine aminotransferase
ANC	absolute neutrophil count
AST	aspartate aminotransferase
BUN	blood urea nitrogen
CBC	complete blood cell (count)
CR	complete response
CRC	Clinical Research Coordinator
CRF	case report form
CT	computerized tomography
CTCEA	Common Terminology Criteria for Adverse Events
CTEP	Cancer Therapy Evaluation Program
CTMS	Clinical Trial Management System
CTV	clinical tumor volume
DFS	disease-free survival
DLT	dose limiting toxicity
DSMC	Data and Safety Monitoring Committee
DSMP	Data and Safety Monitoring Plan
ECOG	Eastern Cooperative Oncology Group
FCBP	female of childbearing potential
FDA	Food and Drug Administration
GCP	Good Clinical Practice
HBV	hepatitis B virus
HCT	hematocrit
HCV	hepatitis C virus

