3.2 STUDY OUTCOMES

3.2.1 Primary Endpoints

Proportion of patients with undetectable serum PSA (< 0.2 ng/mL) at 6 months following completion of apalutamide therapy (18 months from date of randomization).

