10 END OF TREATMENT

A patient may be discontinued from study treatment at any time if the patient or the Investigator feels that it is not in the patient's best interest to continue on study. If a patient's study treatment must be discontinued, this will not result in automatic withdrawal of the patient from the study.

Study treatment with apalutamide will be discontinued for the following reasons, whichever occurs first:

- Disease progression by PCWG criteria. PSA progression is defined as increase of at least 2 ng/mL and 25% above the nadir or baseline on study, whichever is lower, confirmed on repeat measurement at least two weeks later.
- Completion of 13 cycles of study therapy (52 weeks)
- Any episode of seizure
- Any other adverse event that cannot be adequately managed with dose modifications, including dose interruption for treatment-related adverse events that do not improve to Grade 1 or baseline within 14 days, will require study drug discontinuation
- Protocol violation requiring discontinuation of study treatment
- Patient is not compliant with study procedures
- Lost to follow-up
- Patient withdrawal of consent
- Janssen's request for early termination of study

All patients discontinuing study treatment in the absence of disease progression will enter the Post-Treatment Period for PSA monitoring until the time of confirmed PSA progression.

Follow up on study will continue at least the first occurrence of one of the following:

- Disease progression by PCWG criteria.
- Protocol violation requiring discontinuation of study treatment
- Patient is not compliant with study procedures
- Lost to follow-up
- Patient withdrawal of consent
- Janssen's request for early termination of study

If a patient is lost to follow-up, every reasonable effort must be made by the study site personnel to contact the patient and determine the reason for discontinuation/withdrawal. The measures taken to follow up must be documented. When a subject withdraws before completing the study, the reason for withdrawal is to be documented in the CRF and in the source document. Study drug assigned to the withdrawn subject may not be assigned to another subject. Subjects who withdraw will not be replaced.

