12 STATISTICAL METHODS AND CONSIDERATIONS

12.1 ANALYSIS POPULATIONS

Safety Analysis Population [SAFETY]: All patients who receive at least one dose of study drug, with treatment assignments designated according to actual study treatment received will be the primary population for evaluating safety and treatment compliance and administration.

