12.2 ANALYTIC PLAN

12.2.1 Analysis of Primary Endpoint

The primary endpoint for the study is the proportion of patients with undetectable serum PSA (< 0.2 ng/mL) at 6 months following completion of apalutamide therapy (18 months from date of randomization). Fisher's exact test will be used to compare the proportion in the two treatment arms. Patients who discontinue apalutamide prior to completion of 12 months of therapy for reasons other than disease progression by PCWG criteria, as well as patients who withdraw or are lost to follow up, will be considered inevaluable for this analysis. Patients who discontinue treatment for radiographic or clinical progression, even if occurring prior to receipt of SBRT in the experimental arm), would be evaluable for analysis of the primary endpoint.

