12.2.2 Analyses of Secondary Endpoints

Comparison of time to PSA progression will be performed using a two-sided log-rank test. Kaplan-Meier methods will be used to estimate medians for each treatment arm. Cox proportional-hazard models, including the same factors as above, will be used to estimate the hazard ratio and its 95% confidence interval (CI).

Adverse events (AEs) will be graded according to the NCI Common Terminology Criteria for Adverse Events (CTCAE) Version 4.03. All AEs reported from the first dose of study drug until 30 days after the last dose of study drug will be considered as treatment-emergent AEs and will be summarized by treatment arm. For each treatment arm, adverse event incidence rates will be summarized with frequency and percentage, with all patients treated in that treatment arm as the denominator, unless otherwise specified. In addition, AE incidence rates will also be summarized by severity and relationship to study drug. Treatment-related AEs are those judged by the Investigator to be at least possibly related to the study treatment. Adverse events with missing severity or relationship to study drug will be classified as severe and treatment-related, respectively.

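### The only planned analysis of the primary endpoint drops randomised patients because of events after randomisation, and no all-randomised analysis is planned

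*Combined protocol and SAP*

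**What the plan says.** The endpoint is PSA below 0.2 ng/mL "at 6 months following completion of apalutamide therapy (18 months from date of randomization" (Section 3.2.1). Section 12.2.1 compares the arms by Fisher's exact test. Patients who stop apalutamide before 12 months "for reasons other than disease progression by PCWG criteria, as well as patients who withdraw or are lost to follow up, will be considered inevaluable". Patients who stop for radiographic or clinical progression remain evaluable, even if they never reached SBRT. The abstract's statistical paragraph gives the rule for early stoppers only: those who stop for "reasons other than disease progression by PCWG criteria will be considered inevaluable for this analysis".

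Section 12.1 defines one population, all patients with at least one dose. It "will be the primary population for evaluating safety and treatment compliance and administration". No all-randomised set, missing-data rule or sensitivity analysis is given for the primary endpoint.

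Section 10 keeps early stoppers under observation: "All patients discontinuing study treatment in the absence of disease progression will enter the Post-Treatment Period for PSA monitoring". Sections 7.2.1 and 8.6 set PSA every 28 days (+/- 7 days in 8.6). Monitoring ends at progression or new non-protocol therapy (Section 8.6), and at withdrawal, loss, non-compliance, certain protocol violations or early termination (Section 10).

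**The concern.** Section 3.1 says the trial was randomised to learn whether adding SBRT improves outcomes. The planned test compares only patients who completed 12 months of drug or progressed. Membership of that group is settled after assignment is known (Section 5.2: no blinding), and partly by judgement. Treatment may stop whenever the patient or investigator thinks it best (Section 10). Adverse events related to SBRT are a stopping reason (Section 4.3) that one arm alone can meet. Clinical progression, which keeps a patient evaluable, is not defined.

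The rule also sets aside outcomes that are known. Section 10 states: "PSA progression is defined as increase of at least 2 ng/mL and 25% above the nadir or baseline on study, whichever is lower". Take an assumed early stopper with nadir 0.1 and month-18 PSA 1.5 ng/mL. The rise is 1.4, below 2, so he has not progressed and is still monitored. His PSA is not below 0.2, so he is an observed failure, yet he is excluded. An early stopper with PSA below 0.2 at month 18 is an observed success and is excluded too.

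Section 3.1 says a positive result would justify a phase 3 trial. That decision would rest on this subset alone.

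**Working it through.** **Inputs.** From Section 12.2.5: 30 per arm, 10% inevaluable per arm (30 x 0.9 = 27), rates 2.5% (control, C) and 25% (SBRT, S), one-sided Fisher test at 0.10. The documents give no other loss rate, so unequal losses below are assumed illustrations.

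**Formulas.** One-sided p = P(X >= x_S), with X hypergeometric: n_S draws from n_C + n_S patients, of whom x_C + x_S are responders. Rejection probability = sum of Bin(x_C; n_C, p_C) x Bin(x_S; n_S, p_S) over all tables with p <= 0.10.

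**1. The plan's own figure.** 27 per arm, 2.5% vs 25%: 83.6%, against the stated 84%. It reproduces.

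**2. Single tables.**

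| Control | SBRT | p |
|---|---|---|
| 1/30 | 5/30 | 0.097 |
| 1/29 (one control non-responder excluded) | 5/30 | 0.105 |
| 2/30 | 6/30 | 0.127 |
| 2/30 | 6/27 (three SBRT non-responders excluded) | 0.095 |
| 1/27 | 5/27 (equal exclusions from the first row) | 0.096 |

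**3. How often this could matter.** This is the binomial weight, at 2.5% vs 25% and 30 per arm, of tables whose decision changes when one to three non-responders leave one arm only. From SBRT, 3.3% of results become significant. From control, 4.3% become non-significant.

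**4. False positives under the current rule.** Equal true rate p in both arms, all excluded patients non-responders. The evaluable rate is then p/(1 - loss), with n_C = 27 and n_S = 27, 24 or 21.

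| Loss SBRT/control | p=2.5% | 10% | 15% | 25% |
|---|---|---|---|---|
| 10%/10% | 0.3% | 4.7% | 5.3% | 5.3% |
| 20%/10% | 1.8% | 6.7% | 7.2% | 8.4% |
| 30%/10% | 1.8% | 7.1% | 9.7% | 14.9% |
| All 30 per arm counted | 0.3% | 4.8% | 5.5% | 5.6% |

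**5. Power at 2.5% vs 25%, losses unrelated to outcome.** Counting all losses as failures multiplies each rate by (1 - loss) and keeps 30 per arm.

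| Loss SBRT/control | Excluded | All losses as failures |
|---|---|---|
| 10%/10% | 83.6% | 83.3% |
| 20%/10% | 82.2% | 75.5% |
| 30%/10% | 74.6% | 65.3% |
| 10%/30% | 80.1% | 85.9% |

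If every patient is measured and responds at his arm's rate, power is 87.9%.

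**6. Where the alternative can mislead.** No true difference, 30% control and 10% SBRT loss, unrelated to outcome. Losses as failures compares 0.7p with 0.9p at 30 per arm; exclusion compares p with p at 21 and 27. At p = 15%: 10.2% vs 5.5%. At p = 25%: 13.1% vs 5.8%. At p = 2.5% both are about 0.3%.

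**The case against.** The rule is disclosed, and the sample size allows for it. Durability after a completed 12-month course is a coherent phase II question, and Section 3.1 asks only for an intermediate signal. On this view the gap is a missing sensitivity analysis. That is a fair case for keeping the evaluable analysis in the plan. But a budget for exclusions does not make the remaining groups comparable.

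A fixed month-18 endpoint also changes the question for early stoppers. The objective (Section 2.1) counts 6 months from cessation, so for a man who stops at month 2, month 18 is 16 months off drug. This stands, and the fix must deal with it. The calculations also do not favour one rule throughout: step 6 shows that counting losses as failures can mislead, and the tables in step 2 were chosen near the 0.10 boundary.

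Three stronger readings are tempting, and the documents do not support them:

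- A reader might infer that the exclusion favours SBRT or inflates the error rate. No arm-specific loss is given, and only one of the 12 current-rule cells in step 4 exceeds 10%, at ten times the planned control rate.
- A reader might infer that exclusion gains almost no power. That holds near 10% loss in each arm (83.6% vs 83.3%). With heavier SBRT loss it gains 6.7 points (82.2 - 75.5) or 9.3 points (74.6 - 65.3) over counting losses as failures.
- A reader might infer that every early stopper will have a month-18 PSA, or that time to PSA progression has the same exclusion. Monitoring has several earlier end points, so some values will be missing. Section 12.2.2 states no exclusion and no population: "Comparison of time to PSA progression will be performed using a two-sided log-rank test".

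**Conclusion.** The concern holds as a gap that should be fixed; it does not show that the planned result will be wrong. The sole primary analysis conditions on post-randomisation, partly discretionary events, and some PSA values due to be collected are not used. Bias of unknown size and direction is possible.

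The effect is small when losses are similar in the two arms. At the planned control rate, false positives were at most 1.8% in the scenarios tried. The exposure is fragility: with about one responder expected in control (30 x 0.025 = 0.75), one to three one-sided exclusions can move p across 0.10. The 3.3% and 4.3% figures are upper illustrations, because they assume removals from one arm, all of them non-responders, and whichever count from one to three changes the decision.

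The like-for-like contrast in step 4 is 14.9% under exclusion against 5.6% with everyone counted. It rests on an extreme assumption: 30%/10% loss, a 25% rate in both arms, and no responders among the excluded.

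**What to change.** - **Primary analysis (Sections 12.1, 12.2.1, abstract):** all randomised patients by assigned arm, PSA below 0.2 ng/mL at 18 months from randomisation. Use the measured value whatever the apalutamide duration.
- **Window:** state one that fits the 28-day (+/- 7 days) schedule. Consecutive draws can be at most 28 + 7 + 7 = 42 days apart, so +/- 21 days around month 18 always holds a draw if visits are kept. Take the draw nearest month 18.
- **Not undetectable:** prior progression, new anticancer therapy, death, or no PSA in the window.
- **Sensitivity analysis:** keep the present evaluable-patient analysis, prespecified. Report exclusions and missing values by arm and reason. If the team prefers the evaluable analysis as primary, the all-randomised one must at least be prespecified and reported beside it.
- **Wording:** align the abstract and Sections 2.1, 3.2.1 and 12.2.1. Six months after cessation and 18 months from randomisation agree only for patients who complete 12 months. The abstract should also carry the full rule for withdrawals and losses.
- **Power (Section 12.2.5):** about 83% (all losses as failures) to 88% (all measured at their arm's rate), for 10% loss per arm only. Add that it falls to 75.5% at 20% SBRT/10% control loss if all losses count as failures, against 82.2% with exclusion.

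**Cost.** No extra patients or scheduled visits. The team must accept a definition change: month 18 is not 6 months off drug for early stoppers. Counting missing values as failures can itself bias the comparison if control losses are heavier, which is why measured PSA comes first and the evaluable analysis is kept. The change needs a protocol amendment with Protocol Review Committee and IRB approval (Section 13.5).

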Duration of Therapy	
Patients will continue protocol treatment until the first occurrence of one of the following:
 
 • Disease progression by PCWG3 criteria • Unacceptable adverse event(s) related to apalutamide or SBRT • Completion of treatment (52 weeks for apalutamide) • Patients decides to withdraw from the study • Significant patient non-compliance with protocol • General or specific changes in the patients' condition render the patient unacceptable for further treatment in the judgment of the investigator.
Duration of Follow up	Patients will continue on study in follow up until disease progression by PCWG3 or withdrawal from study, whichever occurs first.
Duration of Study	The anticipated study duration is approximately 36 months.
Study Drugs/ Treatments	
 • Apalutamide will be administered orally on a continuous daily dosing regimen, at a starting dose of 240 mg once daily (4 x 60-mg tablets), until the completion of 12 months of treatment, unacceptable toxicity, or PSA progression, whichever occurs soonest. • SBRT will be delivered by treating radiation oncologist according to standard institutional practice for up to 5 PSMA-avid radiation fields. SBRT must be initiated within 90 days following initiation of apalutamide therapy. 
SBRT will be delivered in 1 to 5 fractions, and the dose and fractionation schedule will depend on the size and location of the lesion/radiation field and the surrounding normal tissue constraints in accordance with AAPM Task Group 101 recommendations. Typical doses include 16 – 24 Gy in 1 fraction, 40 – 50 Gy in 4 fractions, and 40 – 60 Gy in 5 fractions.

Safety Assessments	Patients will be assessed for adverse events (AEs) at each monthly clinic visit while on the study treatment. Adverse events will be graded according to the National Cancer Institute (NCI) Common Terminology Criteria for Adverse Events (CTCAE) Version 4.03. Type, incidence, severity, timing, seriousness, and relatedness of AEs, and laboratory abnormalities will be reported.
Efficacy Assessments	Disease assessments will be performed as scheduled according to the calendar, regardless of treatment delays resulting from toxicity. PSA measurements will be performed every 4 weeks until the time of

	PSA progression by PCWG criteria. PSMA-PET imaging will be performed at baseline and is optional at the time of PSA progression.

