4.3 DURATION OF THERAPY

Protocol therapy will continue until the first occurrence of any one of the following:

- Disease progression by PCWG3 criteria
- Unacceptable adverse event(s) related to apalutamide or SBRT
- Completion of treatment (52 weeks)
- Patients decides to withdraw from the study
- Significant patient non-compliance with protocol
- General or specific changes in the patients' condition render the patient unacceptable for further treatment in the judgment of the investigator.

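### The plan gives two rules on whether a man who stops apalutamide early for radiographic or clinical progression is evaluable for the primary endpoint, and never says he counts as a non-responder.

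*Combined protocol and SAP*

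**What the plan says.** Three statements bear on this.

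- **Abstract, Statistical Analysis/Sample Size Justification:** "Patients who discontinue apalutamide prior to completion of 12 months of therapy for reasons other than disease progression by PCWG criteria will be considered inevaluable". No exception follows.
- **Section 12.2.1, third sentence:** the same rule, extended to withdrawals and losses to follow-up. Men who stop apalutamide before 12 months "for reasons other than disease progression by PCWG criteria, as well as patients who withdraw or are lost to follow up, will be considered inevaluable".
- **Section 12.2.1, last sentence:** "Patients who discontinue treatment for radiographic or clinical progression, even if occurring prior to receipt of SBRT in the experimental arm), would be evaluable".

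Only the PSA part of the PCWG criteria is written out. In Section 10, "PSA progression is defined as increase of at least 2 ng/mL and 25% above the nadir or baseline on study, whichever is lower", with confirmation at least two weeks later; Section 7.1.8 says the same. No definition of clinical progression appears.

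Treatment can also end without PCWG progression. Section 4.3 lists, as a separate item, changes in the patient's condition that "render the patient unacceptable for further treatment in the judgment of the investigator". Section 10 opens by allowing a stop whenever the patient or investigator thinks continuing is not in the patient's interest.

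On imaging, the abstract says "PSMA-PET imaging will be performed at baseline and is optional at the time of PSA progression". Appendix 1 schedules no other scan. Section 8.6 ends PSA tracking at PCWG3 progression or at the start of non-protocol therapy. Section 5.2 states that there is no blinding.

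**The concern.** Take a man who stops at month 5 because his cancer is judged to be progressing clinically, without PCWG criteria being met. The abstract and the third sentence of 12.2.1 remove him from the primary analysis; the last sentence of 12.2.1 keeps him. If he is removed, a treatment failure leaves the denominator. If he is kept, the plan still does not say how he scores. Once he starts another therapy his PSA is no longer tracked, so a month-18 value may not exist, and he could be treated either as a failure or as missing.

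The label would be chosen by investigators who know the arm, with no scheduled on-treatment scan to settle it. If the rules are reconciled only after month-18 results are visible by arm, the choice between them could be influenced by the data. Few responders are expected, so a small shift in a denominator can matter when the result is close to the threshold.

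**Working it through.** **1. The plan's own figure.** Inputs from Section 12.2.5: 30 men per arm, 10% inevaluable, 25% v 2.5%, Fisher's exact test, one-sided 0.10. Evaluable per arm: 30 × 0.90 = 27. For x SBRT-arm and y control responders out of n1 and n2,

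p(x, y) = Σ over j ≥ x of C(n1, j) · C(n2, x+y−j) / C(n1+n2, x+y).

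Power is the sum of Bin(x; 27, 0.25) · Bin(y; 27, 0.025) over all pairs with p ≤ 0.10. The result is 83.6%, which matches the stated 84%. Expected responders: 27 × 0.25 + 27 × 0.025 = 6.75 + 0.675, or about 7.4 in total.

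**2. The rules side by side.**

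| Reason for stopping before 12 months | Abstract | 12.2.1, third sentence | 12.2.1, last sentence |
|---|---|---|---|
| Progression meeting PCWG criteria | not excluded | not excluded | evaluable if radiographic or clinical |
| Radiographic or clinical progression not meeting PCWG criteria | inevaluable | inevaluable | evaluable |
| Other early stop, not progression | inevaluable | inevaluable | not addressed |

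The middle row is the conflict. How many men fall in it depends on what the full PCWG3 criteria cover, which the documents do not reproduce.

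**3. Single results near the threshold.** The documents give no number of such men, so these counts are assumptions. Each man removed is a non-responder.

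- 5/27 v 1/27: [C(27,5)·27 + C(27,6)] / C(54,6) = 2,475,720 / 25,827,165 = 0.096. Remove one control man, 5/27 v 1/26: 2,394,990 / 22,957,480 = 0.104.
- 6/27 v 2/27: p = 0.125. Remove one, two or three SBRT-arm men: 0.113, 0.101, 0.090.
- Near the planned result, 7/27 v 1/27: p = 0.025. Remove three control men: 0.037. Remove three SBRT-arm men: 0.016. Neither crosses 0.10.

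**4. How often the verdict changes.** Draw x and y from the two binomials at the planned rates, remove k non-responders, and sum the probability of every pair whose verdict at 0.10 differs before and after.

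| k removed | SBRT arm only | Control arm only | Both arms |
|---|---|---|---|
| 1 | 0.04% | 4.9% | 0.04% |
| 2 | 0.04% | 5.3% | 0.04% |
| 3 | 4.4% | 5.3% | 0.04% |
| 4 | 4.8% | 7.3% | 0.04% |
| 5 | 4.8% | 7.5% | 0.04% |

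Removal from the SBRT arm turns non-significant results significant; removal from the control arm does the reverse.

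**5. Effect on power when both arms lose the same number.** If k men already counted as failures among the 27 are dropped from each arm, the rates become 27 × 0.25/(27 − k) and 27 × 0.025/(27 − k). Power is 83.6% at k = 0 and 84.4% at k = 5.

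**The case against.** The strongest reply is that 12.2.1 is a general rule followed by a specific clarification. The last sentence takes up progression directly, goes as far as men who progress before receiving SBRT, and would do little for men outside PCWG criteria unless it governed the sentence before it. The abstract is an abridgement; it also leaves out the rule on withdrawals and losses to follow-up. This is a fair reading and probably the intended one. It does not remove the problem: the sentence carries no words of exception, the abstract still gives the opposite answer, and clinical progression and responder status remain unstated under either reading.

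Four stronger readings are tempting, and the documents do not support them.

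- A reader might infer that clinical progression lies outside the PCWG criteria. The full PCWG3 criteria are not reproduced, so the documents show only that the term is undefined here.
- A reader might infer that a change-in-condition stop under 4.3 is automatically inevaluable. Section 4.3 makes no such classification. If the actual reason was clinical progression, the last sentence of 12.2.1 would keep the man whichever item was recorded.
- A reader might infer that labelling readily swings the primary test in either direction. That needs one-sided relabelling and a result already close to 0.10.
- A reader might infer a loss of power. With rates held at 25% v 2.5% and k extra men lost per arm beyond the planned 10%, power would run from 81.9% (k = 1) to 72.7% (k = 5). Nothing in the documents says these men fall outside the 10% allowance.

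**Conclusion.** The inconsistency is real and sits in the definition of the primary analysis set. Its likely effect is modest. The sample-size calculation stands, and relabelling equal numbers in both arms is close to harmless. The exposure is to unequal relabelling in an unblinded trial: under an assumed three men in one arm only, the verdict changes in about 4% of trials (SBRT arm) or 5% (control arm). Across one to five men the range is 0.04% to 4.8% and 4.9% to 7.5% respectively. These figures assume the planned rates, 27 evaluable per arm and that every relabelled man is a non-responder; they describe an assumed worst case, not an expected one. The missing statement of responder status is part of the same gap and should be closed with it.

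**What to change.** State one analysis rule in Section 12.2.1 and in the abstract: men who stop apalutamide early for PSA, radiographic or clinical progression are evaluable and count as not having undetectable PSA at month 18, whether or not a month-18 value exists. Define clinical progression for the analysis and have its basis documented on the CRF. Settle each such man's classification before month-18 PSA is tabulated by arm.

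This changes analysis classification only, not when anyone stops treatment. It needs a revised sentence in each of two places, a short definition and, if the CRF does not already capture it, a coded reason for stopping; the CRF is not among the documents. No visits or patients are added. The remaining weakness is that some stops for a change in condition will still need a judgment on cause, so the influence of unblinded labelling is reduced but not removed.
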